7.4 Safety Evaluations and Procedures

The risks and anticipated ADEs for the Nucleus 8 SP, as identified in Sections 8.2 and 8.3 of the CIP, will be assessed in the clinical investigation via reporting of all AEs/ADEs from the time of first subject first visit until last subject last visit.

Safety data adjudication may be conducted by the Sponsor's Medical Officer in accordance with the Sponsor's standard operating procedures.

7.4.1 Concomitant Medication and Therapies

There is potential that concomitant medical treatments may influence the outcomes of this study. All concomitant medical treatments will be collected as part of this study.

7.5 Equipment Used for Evaluation of Performance and Safety

7.5.1 Speech Perception

Speech perception performance in quiet will be assessed using a loudspeaker configuration with the speech from the front (S0).

Speech perception performance in noise will be assessed using a loudspeaker configuration with the speech and noise from the front (S0N0) and with speech from in front and noise to the side of the test ear (S0N90).

The loudspeakers will be located at head height for a seated subject (reference point). The distance from the loudspeaker from the reference point will be approximately one meter. There will be defined locations for the loudspeakers and subject within the test environment.

7.6 Sponsor Role in Conduct of the Clinical Investigation

Sponsor and investigator roles are assumed by Cochlear employees.

Cochlear has designed and will execute this clinical trial in-house at Cochlear Limited, Sydney, at Cochlear Limited, Melbourne and at the Cochlear Technology Centre (CTC) in Mechelen, Belgium. The study sites consist of a small team of Investigators, trained as clinical Audiologists, to execute this research activity. Investigators are qualified audiologists familiar with cochlear implant development, surgery and programming. Investigators' trial materials and testing rooms (sound booths) are securely separated from Sponsor facilities. The trial investigators, or delegates within the study site, will enter the data into the eCRF.

The study is planned, designed and developed by a separate group within Cochlear, known as Clinical Affairs (the Sponsor). Cochlear has SOPs to manage the separation of Investigator and Sponsor activities as well as ensure they align with all applicable regulations.

8 RISKS AND BENEFITS OF THE INVESTIGATIONAL MEDICAL DEVICE AND CLINICAL INVESTIGATION

8.1 Anticipated Clinical Benefits

Study subjects will be asked to use hearing performance features associated with the Nucleus 7 and Nucleus 8 SPs during acute testing sessions, however this is not anticipated to provide benefits to the subject due to the acute nature of the testing.

Clinical Investigation Plan: CLTD5804

Subjects who haven't previously experienced using the ForwardFocus feature may experience benefit of improved communication through reduction of distracting noise while using the feature during the session only.

Due to the limited use of the investigational devices, there are no long-term clinical benefits anticipated for the study subjects.

8.2 Anticipated Adverse Device Effects

Cochlear's internal hazards analysis considers probable hazardous situations relating to the Nucleus 7 and Nucleus 8 SPs.

The risks associated with the Nucleus 7 and Nucleus 8 SPs and Accessories have been identified, analysed and evaluated. The residual risk level has been determined to be as low as possible in accordance with Cochlear's Product Risk Management Procedure and are acceptable.

Subjects may be exposed to the anticipated adverse device related effects associated with use of the Nucleus 7 and Nucleus 8 SPs such as pain or discomfort when wearing the processor and a risk that some sounds could be uncomfortable. Product specific warnings can be found in the respective User Guide and relevant instructions for use.

8.3 Risks Associated with Participation in the Clinical Investigation

There is a small risk that programs on the Nucleus 7 and Nucleus 8 SPs may sound different to each user's own sound processor; this is unlikely if study subjects enter the study already using a Nucleus 7 Sound processor and more likely if they enter a study with a legacy device or an off-the-ear sound processor. If subjects experience sound that is uncomfortable, they are counselled to remove the sound processor off their head or ask the research audiologist to immediately cease stimulation. Other risks may include exacerbation of existing tinnitus and a reduction in the sound quality or intelligibility of the research programs. Subjects are advised to return to their own processor and promptly inform the investigators if these events occur.

Warnings and contraindications

See the Nucleus 7 SP User Guide for all Warnings and Contraindications. (user guides can be found within the 'Support' section of the country specific Cochlear website; www.cochlear.com). AT this preliminary stage in development, the Nucleus 7 SP User Guide will be relevant for Nucleus 8 SP.

8.4 Risk Mitigation

The study investigational devices have been fully tested for safety, and the performance and use of the investigational devices is expected to be similar to the approved Nucleus 7 SP. Risks have been individually reviewed and found to be clinically acceptable based on implemented controls, verification activities, and the relatively low probability of harm. One or more of the following risk control options are applied to each identified risk: inherent safety by design; protective measures in the device itself or in the manufacturing process; Information for safe usage; investigational procedures.

The residual risks related to the investigational device or procedure will be controlled in the following ways:

Clinical Investigation Plan: CLTD5804

- The fitting and use of the Nucleus 8 SP will conducted by a trained audiologist. Test units will be used for a short duration (up to 3 hours) and will be used by adults who are able to indicate discomfort and remove the sound processor from their head.
- If recipients experience any physical discomfort from the device or if the device produces sounds that are uncomfortable, subjects are encouraged to inform the Investigator and return to using their own sound processor.
- Dropped devices should be inspected for external damage before re-use, to ensure there are no sharp edges/corners or rough surfaces.

8.5 Risk-to-Benefit Rationale

The Nucleus 8 Hazards Analysis indicates that the risk portion of the benefit-risk profile of the Nucleus 8 System is acceptable when used as intended by the intended users. The safety, performance, and patient benefits of the Nucleus 8 System are designed to be at least comparable to the approved Nucleus 7 SP and therefore in line with those expected based on the state of the art for the therapy.

9 STATISTICAL CONSIDERATIONS

9.1 General Considerations

See sections 9.2 to 9.10 for statistical considerations.

9.2 Endpoints

For speech in noise (AuSTIN/LIST) endpoints, two (AuSTIN) or 3 (LIST) lists of sentences will be measured per sound processor condition, and the two dB SRT values will be averaged to produce a single value per condition, per subject.

For speech in quiet (CNC/NVA) endpoints, two (CNC) or three (NVA) lists of words will be measured per sound processor condition, and the two percentage words correct values will be averaged to produce a single value per condition, per subject.

9.2.1 Primary Endpoint

The primary efficacy measure for the Nucleus 8 Sound processor will be Speech Reception Thresholds (SRT) assessed via AuSTIN/LIST Sentence scores in spatially separated adaptive noise.

The primary efficacy outcome for the study will be determined by the following primary efficacy endpoint:

 Paired difference in dB SRT (AuSTIN/LIST) between the Nucleus 8 Sound Processor with ForwardFocus On (BEAM) and the Nucleus 7 Sound Processor with ForwardFocus On (commercial version) (S0N90 4TB).

9.2.2 Secondary Endpoints

Secondary efficacy measures will be the percentage words correct as assessed by CNC, NVA Monosyllabic word scores in quiet.

Clinical Investigation Plan: CLTD5804

Secondary efficacy outcomes for will be determined by the following endpoints:

- Paired difference in percentage CNC/NVA Words correct in quiet (50 dB) with the Nucleus 8 Sound Processor (SNR-NR on) and Nucleus 7 Sound Processor (SNR-NR on)
- Paired difference in percentage CNC/NVA Words correct in quiet (50 dB) with the Nucleus 8 Sound Processor and Nucleus 7 Sound Processor (SNR-NR off)
- Paired difference in percentage CNC/NVA Words correct in quiet with the Nucleus 8 Sound Processor (Moderate) and Nucleus 7 Sound Processor (Standard directionality)

An additional secondary efficacy measure will be Speech Reception Thresholds (SRT) assessed via AuSTIN Sentence scores in spatially separated adaptive noise according to the following endpoint:

 Paired difference in dB SRT (AuSTIN/LIST) between the Nucleus 8 Sound Processor with ForwardFocus On (BEAM) and the Nucleus 7 Sound Processor with ForwardFocus On (commercial version) (S0N0 4TB).

9.2.3 Exploratory Endpoints

There are no exploratory endpoints

9.3 Hypotheses

For the non-inferiority test of SRT sentences for both primary and secondary endpoints, the 95% CI (alpha=0.025 one-sided) for the mean paired difference (i.e., 'Nucleus 8 SP' versus 'Nucleus 7 SP') will be calculated. If the upper limit of the 95% CI of the mean paired difference is lower than 1dB, the 'Nucleus 8 SP' is regarded as non-inferior to 'Nucleus 7 SP' on that measure.

For the non-inferiority test of CNC/NVA word score, the 95% CI (alpha=0.025 one-sided) for the mean paired difference (i.e., 'Nucleus 8 SP' versus 'Nucleus 7 SP') will be estimated. If the lower limit of the 95% CI of the mean paired difference is above -10%, 'Nucleus 8 SP' is regarded as non-inferior to 'Nucleus 7 SP' on that measure.

9.3.1 Primary Hypotheses

Endpoint: Paired difference in dB SRT (AuSTIN/LIST) between the Nucleus 8 Sound Processor with ForwardFocus On (BEAM) and the Nucleus 7 Sound Processor with ForwardFocus On (commercial version) (S0N90 4TB).

H0: Sentence in noise (S0N90 4TB) scores (dB SRT) with the Nucleus 8 Sound Processor with FF On (treatment) are inferior to those with the Nucleus 7 Sound Processor with FF On (control)

Nucleus 8 FF ON – Nucleus 7 FF OFF ≥ 1 dB (NB: higher SRT scores represent poorer performance)

H1: Sentence in noise (S0N90 4TB) scores (dB SRT) with the Nucleus 8 Sound Processor with FF On (treatment) are non-inferior to those with the Nucleus 7 Sound Processor with FF On (control)

Nucleus 8 FF ON - Nucleus 7 FF OFF < 1 dB

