Direct Streaming Choice	Android iPhone	Android* iPhone* Bluetooth 5.2 Hearing Aid Profile*
Wireless Accessory support	Prox 2	Prox 2*
Input Processing Technologies	BEAM SNR-NR WNR FF with Zoom Whisper	BEAM SNR-NR WNR* FF with standard FF with Zoom FF with BEAM Whisper* SCAN X*
Core Control: Processor, CR310*, Nucleus Smart App*.		
Core Connected Care: Remote Check*-ready, CS Pro programming software		

22 of 77

Table 2 Speech perception comparisons and rationale

Test condition	Comparison	Rationale
CNC/NVA words	Treatment: Nucleus 8	
in Quiet (50 dB	standard directionality SNR-	
SPL)	NR on	
	Control: Nucleus 7 standard	
	directionality SNR-NR on	
	Treatment: Nucleus 8	
	standard directionality SNR-	
	NR off	
	Control: Nucleus 7 standard	
	directionality SNR-NR off	
	Treatment: Nucleus 8	Previous evidence with ForwardFocus (FF) in quiet has shown a small decrease
	standard directionality FF	in performance in quiet (5% at 50 dB SPL) with a 'Strong' attenuation setting
	(Moderate)	(CLTD5606).
		It is predicted that ForwardFocus with a Moderate maximum attenuation setting
		will produce a non-inferior result when compared with Nucleus 7 for words in
	Control: Nucleus 7 standard	quiet (S0).
	directionality	
Sentences in	Treatment: Nucleus 8 BEAM	Previous evidence with FF in S0N0 has shown:
noise S0N0 4-	directionality + FF (GT0,	A decrement compared to Nucleus 6 SCAN when FF was coupled with
talker babble (65	Strong)	BEAM (GT3) (CRC5589)
dB SPL)		(/(/

Test condition	Comparison	Rationale	
	Control: Nucleus 7 Zoom directionality + FF (GT0, Strong)	 A non-inferior result compared to Nucleus 6 SCAN when FF was coupled with Zoom (GT0) (CLTD5606) A benefit compared to Nucleus 6 BEAM when FF was coupled with BEAM (GT3) (unpublished Kiel data) The combination of GT0+BEAM with ForwardFocus is predicted to resolve this performance issue. 	
Sentences in noise S0N90 4-talker babble (65 dB SPL)	Treatment: Nucleus 8 BEAM directionality +FF (GT0, Strong) Control: Nucleus 7 Zoom directionality + FF (GT0, Strong)	Previous evidence with BEAM in S0N+/-90 showed a significant speech perception improvement over Zoom when measured in non-fluctuating speech-spectrum shaped noise ² . There is no known published evidence with FF in S0N90 however a significant improvement is expected over commercially available settings due the ability of the adaptive beamformer to steer the null to more locations than the fixed directionality Zoom, as currently implemented with Nucleus 7.	

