6 OBJECTIVES

6.1 Primary Objective

To characterise adult cochlear implant speech perception in spatially separated speech and noise (S0N90) with the Nucleus 8 SP with ForwardFocus ON (BEAM) compared with the Nucleus 7 Sound Processor with ForwardFocus ON (commercial version)

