Table 3. Speech in Quiet test conditions. NB Whisper and WNR will be off, ADRO and ASC will be on per user preference.

	Expander	SNR-NR	Directionality	ForwardFocus
Nucleus 8 Expander	✓		Std	
Nucleus 7 SNR-off			Std	
Nucleus 8 SNR on		✓	Std	
Nucleus 7 SNR-on		✓	Std	
Nucleus 8 std FF		~	Std	✓(Moderate)

All subjects will be tested in the unilateral condition and each subject will have their contralateral ear (non-test ear) blocked with an EAR plug for all test conditions. Subjects with bilateral implants that meet the inclusion criteria will be tested using the subject's preferred ear or if the preferred ear is not known then the first implanted ear will be used as the testear.

The subject will be positioned so that the middle-point of two ears is centred at the reference point of the sound field. The loudspeaker should be positioned at the same height as the middle-point of the two ears.

The test material will be presented via software on a PC or laptop. The investigator, or suitably qualified delegate will use the software to select:

- CNC/NVA word test
- 50 dB SPL presentation level
- Signal from in front (0 degrees)
- 2 lists (CNC) or 3 lists (NVA) per condition

At the end of each run, the investigator will record the result on the worksheet and in the EDC.

End of visit and return of study devices

After the speech perception evaluation has been completed, study subjects will return the study devices and will use their own device as normal in their home environment in between speech evaluation study visits.

Visit 2

Included in this visit:

- SP fitting and optimisation
- Sound Quality

- Speech in noise testing (S0N0 and S0N90)
- Return devices and study completion

Table 4. Speech in Noise test conditions (S0N0 and S0N90). NB Whisper and WNR will be off, ADRO and ASC will be on per user preference.

	Gain Threshold	SNR-NR	Directionality	ForwardFocus
Nucleus 8 FF+BEAM	0	~	BEAM	✓ (Strong)
Nucleus 7 FF	0	✓	Zoom	✓ (Strong)

Sentence in noise test (S0N0)

In booth speech perception testing will be conducted using the signal processing combinations and hardware listed in Table 4. The order of testing will be conducted according to the counterbalancing outlined in Section 7.2.7.

For S0N0 and S0N90 speech in noise tests, all subjects will be tested in the unilateral condition and each subject will have their contralateral ear (non-test ear) blocked with an ear plug for all test conditions.

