Nucleus 8 FF ON – Nucleus 7 FF OFF ≥ 1 dB (NB: higher SRT scores represent poorer performance)

H1: Sentence in noise (S0N0 4TB) scores (dB SRT) with the Nucleus 8 Sound Processor with FF On (treatment) are non-inferior to those with the Nucleus 7 Sound Processor with FF On (control)

Nucleus 8 FF ON - Nucleus 7 FF OFF < 1 dB

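### Do the protocol's four SRT inequalities, which subtract Nucleus 7 FF OFF, change the comparator of the primary non-inferiority test?

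*Protocol*

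**What the plan says.** Protocol 9.3.1 gives the primary hypotheses twice, once in words and once as an inequality. In words, the null is that Nucleus 8 scores "are inferior to those with the Nucleus 7 Sound Processor with FF On (control"; the worded alternative names the same control. The inequality under the null is "Nucleus 8 FF ON – Nucleus 7 FF OFF ≥ 1 dB (NB: higher SRT scores represent poorer performance". Secondary endpoint 4 in 9.3.2 repeats the pattern: FF on in the words, then "Nucleus 8 FF ON - Nucleus 7 FF OFF < 1 dB" as the alternative.

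Elsewhere the comparator is stated consistently:

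- Protocol 6.1 sets the aim as a comparison of Nucleus 8 "compared with the Nucleus 7 Sound Processor with ForwardFocus ON (commercial version".
- Protocol 9.2.1 defines the primary endpoint as the paired difference between Nucleus 8 with FF on (BEAM) "and the Nucleus 7 Sound Processor with ForwardFocus On (commercial version) (S0N90 4TB".
- Protocol 9.2.2 defines the co-located noise endpoint the same way, "and the Nucleus 7 Sound Processor with ForwardFocus On (commercial version) (S0N0 4TB".
- Table 2 gives the control for both noise configurations as "Control: Nucleus 7 Zoom directionality + FF (GT0, Strong".
- Table 4 lists two noise conditions, one per processor, both with FF at the Strong setting.
- SAP 4.2.2 and 4.2.3 write Nucleus 7 FF ON in all four corresponding inequalities.

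**The concern.** In a non-inferiority trial the margin has meaning only against a named control, and these are the lines where the primary hypothesis attaches 1 dB to a control. A wrong control there would be a wrong hypothesis. FF OFF is also not an empty label: Protocol 4.2.2, describing an earlier study of FF on Nucleus 7, uses it for the default SCAN program and reports FF on as superior in babble from the rear. If FF also helps in the configurations tested here, FF off would be the easier comparator, and a 1 dB margin against it would be looser than a 1 dB margin against FF on.

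A further reason for care is that the SAP, which has the label right, states that it is based on CIP version 1.0, whereas the protocol's change history runs to version 3.0. The wrong label therefore sits in the later document.

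**Working it through.** **1. Which label is intended?**

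| Place | Nucleus 7 comparator in noise |
|---|---|
| Protocol 9.3.1, inequalities (2) | FF OFF |
| Protocol 9.3.2, secondary endpoint 4, inequalities (2) | FF OFF |
| Worded H0 and H1 beside those four lines | FF on |
| Synopsis and Protocol 6.1, 6.2 | FF on |
| Protocol 9.2.1, 9.2.2 | FF on |
| Tables 2 and 4 | FF on (Zoom, Strong) |
| SAP 4.2.2, 4.2.3, inequalities (4) | FF on |

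The change history records no change of comparator. Its only entry touching the hypotheses is the addition of the Flemish speech tests.

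**2. Could the literal inequality be evaluated?** Protocol 7.3 says noise testing uses the Table 4 combinations, which are Nucleus 8 FF with BEAM and Nucleus 7 FF with Zoom. Nucleus 7 without FF is tested only in quiet (Table 3), scored in percent words correct, which cannot be subtracted from a dB SRT. No FF-off SRT will exist.

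**3. What does the decision rule use?** Protocol 9.3 and 9.6 and SAP 4.5 all compare the upper 95% confidence limit of the mean paired difference with 1 dB. None mentions FF off. The paired difference is the one defined in 9.2.1 and 9.2.2.

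**4. Does the sample size depend on the label?** Inputs from Protocol 9.4 are margin 1 dB, SD of paired differences 1.36 dB, one-sided alpha 0.025 and power 0.8. The true difference is not stated; 0 is assumed.

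- Normal approximation: n = (1.36 × (1.960 + 0.842) / 1)² = 14.52, rounded up to 15.
- Paired t with the non-central t distribution, non-centrality √n × 1/1.36: power is 0.785 at n = 16, 0.812 at n = 17 and 0.877 at n = 20. The smallest n reaching 0.80 is 17, the stated figure.

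None of these inputs refers to FF off, so correcting the label leaves 17 unchanged.

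**5. What would be at stake if FF-off data existed?** Let b be the SRT benefit of FF on Nucleus 7 in dB. The documents give no value for these configurations, so b is an assumption. Since lower SRT is better, Nucleus 7 off = Nucleus 7 on + b, and

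Nucleus 8 − Nucleus 7 off < 1 is equivalent to Nucleus 8 − Nucleus 7 on < 1 + b.

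With Nucleus 8 truly 1 dB worse than Nucleus 7 FF on, n = 17 and SD 1.36, the chance of declaring non-inferiority would be:

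| b (dB, assumed) | Effective margin (dB) | Chance |
|---|---|---|
| 0.25 | 1.25 | 0.106 |
| 0.5 | 1.5 | 0.297 |
| 1.0 | 2.0 | 0.812 |
| 1.5 | 2.5 | 0.989 |

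The nominal rate is 0.025. A real switch of comparator would therefore matter a great deal. Steps 2 and 3 show that no such switch can occur in this trial.

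**The case for a change.** The best argument for acting is that the primary hypothesis of a non-inferiority study should be unambiguous on its own line, that FF OFF names a real program, and that replacing one word in four places costs almost nothing. Agreement with the SAP is also weaker support than it looks, because the SAP was written against an earlier protocol version.

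The textual part stands: the contradiction is real, it occurs in all four inequalities, and it is not an artefact of the PDF. The rest does not carry through. To adopt the FF-off reading, a reader would have to set aside the sentence immediately above each inequality, the endpoint restated in the same subsection, both tables and the SAP, and rely on a condition from a different study. Even then there would be no data to analyse. The SAP's version lag does not matter here, because version 3.0 of the protocol settles the comparator from its own text. Nor does the slip leave an analyst a choice to make after seeing results, since only one noise comparison per configuration can be formed.

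**Conclusion.** This is a clerical slip and needs no change to the plan. Four of the protocol's four SRT inequalities carry the wrong label, and every other statement of the comparison carries the right one. An analyst following either document would compute the same paired difference from the same two conditions, test it against the same 1 dB limit and reach the same conclusion. The numerical effect is zero, and the required 17 subjects (20 enrolled) is unaffected.

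The conclusion rests on Table 4 being the full list of noise conditions, which Protocol 7.3 supports. The sample-size check also assumes a true difference of 0. Tidying the label if the protocol is reissued for other reasons would be copy-editing; nothing in the conduct or analysis depends on it.

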9.3.2 Secondary Hypotheses

Secondary endpoint 1

Paired difference in percentage CNC/NVA Words correct in quiet (50 dB) with the Nucleus 8 Sound Processor (SNR-NR on) and Nucleus 7 Sound Processor (SNR-NR on)

H0: Words in quiet (50 dB CNC/NVA words) scores (% words correct) with the Nucleus 8 Sound Processor SNR-NR on (treatment) are inferior to those with the Nucleus 7 Sound Processor SNR-NR on (control)

Nucleus 7 SNR-NR ON – Nucleus 8 SNR-NR ON ≤ -10%

H1: Words in quiet (50 dB CNC/NVA words) scores (% words correct) with the Nucleus 8 Sound Processor SNR-NR on (treatment) are non-inferior to those with the Nucleus 7 Sound Processor SNR-NR on (control)

Nucleus 7 SNR-NR ON - Nucleus 8 SNR-NR ON > -10%

Secondary endpoint 2

Paired difference in percentage CNC/NVA Words correct in quiet (50 dB) with the Nucleus 8 Sound Processor and Nucleus 7 Sound Processor (SNR-NR off)

H0: Words in quiet (50 dB CNC/NVA words) scores (% words correct) with the Nucleus 8 Sound Processor (treatment) are inferior to those with the Nucleus 7 Sound Processor SNR-NR off (control)

Nucleus 7 SNR-NR Off – Nucleus 8 ON ≤ -10%

H1: Words in quiet (50 dB CNC/NVA words) scores (% words correct) with the Nucleus 8
Sound Processor (treatment) are non-inferior to those with the Nucleus 7 Sound
Processor SNR-NR off (control)

Nucleus 7 SNR-NR Off – Nucleus 8

Secondary endpoint 3

Paired difference in percentage CNC/NVA Words correct in quiet with the Nucleus 8 Sound Processor (Moderate) and Nucleus 7 Sound Processor

H0: Words in quiet (50 dB CNC/NVA words) scores (% words correct) with the Nucleus 8 Sound Processor FF Moderate (treatment) are inferior to those with the Nucleus 7 Sound Processor std (control)

Nucleus 7 std – Nucleus 8 FF Moderate ≤ -10%

H1: Words in quiet (50 dB CNC/NVA words) scores (% words correct) with the Nucleus 8 Sound Processor FF Moderate (treatment) are non-inferior to those with the Nucleus 7 Sound Processor std (control)

Nucleus 7 std - Nucleus 8 FF Moderate > -10%

Clinical Investigation Plan: CLTD5804

Secondary endpoint 4

Paired difference in dB SRT (AuSTIN/LIST) between the Nucleus 8 Sound Processor with ForwardFocus On (BEAM) and the Nucleus 7 Sound Processor with ForwardFocus On (commercial version) (S0N0 4TB).

H0: Sentence in noise (S0N0 4TB) scores (dB SRT) with the Nucleus 8 Sound Processor with FF On (treatment) are inferior to those with the Nucleus 7 Sound Processor with FF On (control)

Nucleus 8 FF ON – Nucleus 7 FF OFF ≥ 1 dB (NB: higher SRT scores represent poorer performance)

H1: Sentence in noise (S0N0 4TB) scores (dB SRT) with the Nucleus 8 Sound Processor with FF On (treatment) are non-inferior to those with the Nucleus 7 Sound Processor with FF On (control)

Nucleus 8 FF ON - Nucleus 7 FF OFF < 1 dB

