9.6 Primary Endpoint Analyses

Primary and Secondary Speech Perception Endpoints:

SRT sentence scores in noise and words in quiet scores at different speech testing conditions will be listed and summarised descriptively by treatment group and study population. A Scatter plot or similar plot will be used to present the individual data by treatment group, and bar chart will be used to present the average paired difference and its standard error.

For the non-inferiority test of SRT sentence scores the 95% CI (alpha=0.025 one-sided) for the mean paired difference will be estimated. If the upper limit of the 95% CI of the mean paired difference is lower than 1dB, the treatment condition is regarded as non-inferior to the control in term of SRT sentence perception. The non-inferiority margin of 1dB for SRT is based on clinical consensus.

The same analysis method will be applied to the non-inferiority test for words in quiet scores (monosyllables). For the non-inferiority test of words in quiet scores, the 95% CI (alpha=0.025 one-sided) for the mean paired difference will be estimated. If the lower limit of the 95% CI of the mean paired difference is above -10%, the treatment condition is regarded as non-inferior to the control in

Clinical Investigation Plan: CLTD5804

term of words in quiet perception. The non-inferiority margin of -10% for words in quiet scores (monosyllables) is also based on clinical consensus.

Only when the non-inferiority test for the above specified endpoint is successful, then a superiority test for the endpoint will be further conducted to assess the treatment effect.

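### Protocol 9.3.2 prints the word-score non-inferiority hypotheses for secondary endpoints 1 to 3 with the subtraction reversed (Nucleus 7 minus Nucleus 8 against -10%)

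*Protocol*

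**What the plan says.** Secondary endpoints 1 to 3 compare percent words correct in quiet between the two processors. In protocol 9.3.2 the wording of each null hypothesis is that Nucleus 8 (treatment) is inferior to Nucleus 7 (control), and of each alternative that it is non-inferior. The formulas beneath the wording are:

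- Endpoint 1, H0: "Nucleus 7 SNR-NR ON – Nucleus 8 SNR-NR ON ≤ -10" per cent; H1: "Nucleus 7 SNR-NR ON - Nucleus 8 SNR-NR ON > -10" per cent.
- Endpoint 2, H0: "Nucleus 7 SNR-NR Off – Nucleus 8 ON ≤ -10" per cent. The H1 line has no legible bound in the text available, and no error is claimed for it.
- Endpoint 3, H0: "Nucleus 7 std – Nucleus 8 FF Moderate ≤ -10" per cent; H1: "Nucleus 7 std - Nucleus 8 FF Moderate > -10" per cent.

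The decision rule in protocol 9.3 compares Nucleus 8 with Nucleus 7 and reads "If the lower limit of the 95% CI of the mean paired difference is above -10%, 'Nucleus 8 SP' is regarded as non-inferior". Protocol 9.6 repeats the limit for treatment against control: "If the lower limit of the 95% CI of the mean paired difference is above -10%, the treatment condition is regarded as non-inferior". SAP 4.2.3 prints all three word-score endpoints as Nucleus 8 minus Nucleus 7 against -10%. For the primary endpoint, protocol 9.3.1 also puts Nucleus 8 first ("Nucleus 8 FF ON – Nucleus 7 FF OFF ≥ 1 dB", cited here only for the order of the terms), and secondary endpoint 4 does the same.

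**The concern.** On a score where higher is better, inferiority by the margin means that Nucleus 8 minus Nucleus 7 is -10 points or lower. The five complete formulas in 9.3.2 subtract the other way and keep the same bound, so each states the opposite of the sentence above it.

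This matters because 9.3.2 holds the protocol's only explicit subtraction for word scores. Section 9.3 says versus rather than minus, and 9.6 names no order. An analyst who took the difference from 9.3.2 and the limit from 9.6 would run the test backwards. The SAP has the sign right, but it is based on CIP version 1.0 and its hypotheses name only CNC words, so it does not formally amend the current protocol, which adds NVA words.

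SAP 4.5 also places these endpoints in a fixed-sequence test running from the primary endpoint to secondary endpoint 4. A reversed test on endpoints 1 to 3 would therefore also decide wrongly whether later endpoints may be tested.

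**Working it through.** **1. The plan's own figure.** The only sample-size calculation (protocol 9.4, SAP 4.1) is for SRT: margin 1 dB, SD of differences 1.36 dB, one-sided alpha 0.025, power 0.8, n = 17. For a paired t-test at zero true difference, the non-central t gives power 0.785 at n = 16 and 0.812 at n = 17. The stated 17 is reproduced. It uses no word-score input, so the sign of the word-score hypotheses does not affect it.

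**2. Direction.** Let D = Nucleus 8 minus Nucleus 7, in percentage points.

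- Printed H0: Nucleus 7 minus Nucleus 8 ≤ -10, so -D ≤ -10, so D ≥ +10. Nucleus 8 is at least 10 points better.
- Printed H1: -D > -10, so D < +10. This holds at D = -10, -15 or -20, all of which are inferior by the plan's own margin.
- Verbal H0 and SAP 4.2.3: D ≤ -10. Verbal H1 and SAP 4.2.3: D > -10.
- The rule in 9.3 (lower limit above -10% means Nucleus 8 is non-inferior) is valid only when the interval is for D.

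This step needs no assumption.

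**3. Consequence if the -10% lower-limit rule is applied to the difference as 9.3.2 prints it.** Let δ be the true mean of the difference as taken: δ = D with the correct sign, δ = -D with the printed sign.

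P(pass) = 1 - F(t(0.975, n-1); n-1, λ), with λ = (δ + 10)√n / SD and F the non-central t distribution function.

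Inputs: n = 17 or 20 (protocol 9.4) and one-sided alpha 0.025 (protocol 9.3). The documents give no SD for word-score differences, so 7 to 15 points is assumed. For scale, sampling error from the number of words alone, at 50% correct, gives

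- CNC, 2 × 50 words: 100 × √(2 × 0.25 / 100) = 7.07
- NVA, 3 × 11 words: 100 × √(2 × 0.25 / 33) = 12.31

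Worked case: n = 17, SD 15, D = -10. Printed sign: λ = 20 × √17 / 15 = 5.50, P = 0.999. Correct sign: λ = 0, P = 0.025.

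Probability of declaring non-inferiority, printed sign / correct sign:

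| n | SD | D = -10 | D = -5 | D = 0 | D = +10 |
|---|---|---|---|---|---|
| 17 | 7 | 1.000 / 0.025 | 1.000 / 0.790 | >0.999 both | 0.025 / 1.000 |
| 17 | 15 | 0.999 / 0.025 | 0.972 / 0.252 | 0.733 both | 0.025 / 0.999 |
| 20 | 7 | 1.000 / 0.025 | 1.000 / 0.858 | >0.999 both | 0.025 / 1.000 |
| 20 | 15 | >0.999 / 0.025 | 0.989 / 0.293 | 0.807 both | 0.025 / >0.999 |

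Simulation with 200,000 trials per cell agrees. At D = 0 the two signs pass equally often, so a check of the program under equality would not reveal the reversal.

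**The case against.** The strongest reply is that the rule which decides the result already runs the right way. Protocol 9.3 compares Nucleus 8 with Nucleus 7, the verbal hypotheses are correct, and SAP 4.2.3 prints the correct subtraction. An analyst would have to set all three aside to run the test in reverse. In 9.6 the order is implied, because a lower limit above -10% shows non-inferiority on a higher-is-better score only for treatment minus control. SAP 4.5 states the word-score rule for monosyllables generally, so in practice it reaches NVA words although SAP 4.2.3 does not name them. On this view the matter is one of notation.

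Much of that stands. The pass rates above are not operating characteristics of the analysis as the SAP describes it; they show what happens if 9.3.2 is followed literally. Two supporting points also need limits:

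- The D = -5 column uses the loss that Table 2 reports for the Strong ForwardFocus setting. Endpoint 3 tests the Moderate setting, for which Table 2 predicts non-inferiority, so the column is an illustration and not a forecast.
- The word-count SDs are for 50% correct, where that component is largest. At 80% correct they are 100 × √(2 × 0.16 / 100) = 5.7 for CNC and 100 × √(2 × 0.16 / 33) = 9.8 for NVA.

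None of this makes the printed formulas right. Five complete inequalities state the reverse of the sentences they formalise, and correct text elsewhere does not amend them.

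**Conclusion.** The concern holds. The H0 formulas for endpoints 1, 2 and 3 and the H1 formulas for endpoints 1 and 3 have the wrong sign. This follows from algebra and from the documents' own text, with no assumption.

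The practical consequence is conditional on the sign being taken from 9.3.2. In that case, for n = 17 to 20 and an assumed SD of 7 to 15 points:

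- Nucleus 8 truly 10 points worse passes 99.9% to 100% of the time, against 2.5%.
- Nucleus 8 truly 5 points worse passes 97% to 100% of the time, against 25% to 86%.
- Nucleus 8 truly 10 points better passes 2.5% of the time, against 99.9% to 100%.

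The correction should be made, but because the rule in 9.3 and the SAP hypotheses are the right way round, it is not a fault in the primary analysis or in the design.

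**What to change.** In protocol 9.3.2, print secondary endpoints 1 to 3 as in the SAP:

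- H0: Nucleus 8 minus Nucleus 7 ≤ -10 percentage points
- H1: Nucleus 8 minus Nucleus 7 > -10 percentage points

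State the subtraction as Nucleus 8 minus Nucleus 7 explicitly in 9.3 and 9.6. For the endpoint 2 alternative, confirm in the source document that it has the same form.

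The cost is a wording correction, documented as an amendment with the ethics committee notification that protocol section 18 requires (and regulator notification if applicable). Data collection, the sample size and the SAP hypotheses do not change.
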